#### 4.1.5 Phase 3 Community Pilot Inclusion Criteria

Must meet the following eight criteria:

1. Male or assigned male at birth (YTW)
2. Identifies as a man who has sex with men (YMSM) and/or gay bisexual man or transgender woman/transwoman
3. Identifies as African American/Black, Hispanic/Latino, and/or as a racial/ethnic minority or person of color
4. 16-24 years old
5. English-speaking (primary)
6. Currently unemployed but seeking employment or employed only part-time 35 hrs or less on avg/wk)
7. Able to attend a 4-session employment program
8. Did not participate in Phase 2 pilot

## 4.2 Exclusion Criteria

### 4.2.1 Focus Groups

Must not meet any of the following:

1. Individuals identify as non-Hispanic White
2. Individuals not assigned male at birth

#### 4.2.2 Community Advisory Board Exclusion criteria:

Must not meet any of the following:

1. Under age 18
2. White, Asian, Native American, and any other ethnic group not Black or Latino

There are no exclusions regarding sex/gender for the Community Advisory Board.

#### 4.2.3 Intervention Pilot-Test Exclusion Criteria

Must not meet any of the following:

1. Individuals identify as non-Hispanic White
2. Individuals not assigned male at birth
3. Phase 2 only: Individuals with a known HIV positive-status at baseline

### 4.3 Recruitment and Screening

**Recruitment.** Study participants will be recruited by research assistants (RAs) and study recruiters who are also members of the target population. For the CAB, focus groups, and key informant interviews, participants will be recruited by the RAs through pre-existing network connections, including the Chicago Center for HIV Elimination and snowball sampling. Planned recruitment strategies for LGBT-Inclusive Employers also include attending LGBTQ job fairs and emailing LGBTQ non-profits, LGBTQ-owned small businesses, and employers in the Human Rights Campaign Corporate Equality Index or Out & Equal, LGBT CareerLink lists.

For the pilot interventions, participants will be recruited actively by RAs and study recruiters in primary and community clinics serving YMSM and YTW of color, and local gathering places and events for YMSM and YTW such as night clubs, House & Ball events, and other public places that serve the LGBT community (e.g., LGBT centers). Additionally, participants will be asked to refer friends or acquaintances that may be eligible. Passive recruitment will include posting study flyers and posters, and describing the study on Facebook and other social media websites.

### 4.4 Informed Consent

**Consent Process.** Eligible study participants will be taken through the informed consent process in a private room. RAs will review the consent process to make a formal assessment of the participant's decisional capacity to consent prior to signing using a 2-step process. First, the RA will determine if the person understands the study goals by asking "Can you tell me what this study is about?" In step 2, potential participants will be asked questions designed to assess their capacity to understand, appreciate, reason with, and express a choice about participation in our specific protocol. Participants are asked to: (1) name things they will be expected to do during the study; (2) explain what they would do if they no longer wished to participate in the study; (3) explain what they would do if they experienced distress during the study; and (4) identify potential risks for participating in the study. Respondents will be enrolled only if they are able to provide clear and correct answers to each of these items. If study staff feels there is a question about the need for a more formal assessment of the decisional capacity of a potential participant, they will contact the Project Lead or other senior staff. Additionally, study staff will inform the person that the research study is voluntary and their decision whether or not to participate will not impact their relationship with the research site or any subsequent participation in research studies or care provided by the study site. If they agree to participate, they will be immediately enrolled in the study (Appendix VI).

**Parental Consent.** We will not require parental consent for study enrollment and participation. Parental consent may decrease participation rates because some youth will fear that they may be “outed” as a result of participation. Disclosure of sexual orientation or gender identity may place participating youth at risk for parental harassment, abuse or expulsion from the home. The nature and scope of the proposed research do not pose more than “minimal risk” to participants (45 CFR Part 46.102): “the probability and magnitude of harm or discomfort anticipated in the research are not greater in and of themselves than those ordinarily encountered in daily life or during the performance of routine physical or psychological examinations or tests.” Study measures are standard in this population, as are waivers of parental permission for survey and interview studies. Additionally, risk behavior assessments will be based on the National Youth Risk Behavior Survey 2015, which has been administered to youth in 9th to 12th grade. HIV/STI testing is also common (and encouraged) among this group, and does not require parental permission or notification in the state of Illinois.

To compensate for waiver of parental consent participants receive a formal individual assessment of capacity to consent (above) to ensure their understanding of study goals, procedures, and risks from disclosure of sensitive information (see Consent Process). Consistent with national policy recommendations from the Society for Adolescent Medicine, requiring parental permission for the proposed study would have a number of possible negative effects, including: (1) reducing the validity of the findings by effectively eliminating potential participants unwilling to share permission forms with their parents/guardians; (2) increasing risk to some youth whose parents have a negative response to the material in the permission forms that would (correctly) suggest their child has a minority or alternative gender identity; and (3) adding little in the way of actual subject protection, given the minimal risk of study participation.

#### 4.5 Contact Information

Once consented, study staff will complete a Contact Information Form with the participant. Participants will be asked to provide a working phone number or valid email address through which they can be reached, and if messages can be left at or texted to the numbers provided. Study staff will not leave or send messages unless expressly permitted to do so by the. If permission is given to leave phone messages, site staff will assure participants that any messages left with a family member or friend will only ask the participant to contact study staff and will not include any protected health information or information related to study participation.

The Contact Information Form will not contain any study data and will be maintained under double locks at the study site, separate from all study records, with access limited to designated site research personnel.

#### 4.6 Co-enrollment Guidelines

Studies that open after this protocol is implemented can be considered for co-enrollment either by requesting a blanket, one-time approval from the protocol team or by requesting case-by-case permission for co-enrollment in writing from the protocol chair.

### 5.0 STUDY PROCEDURES

**Aim 1: Determine the essential components of a theoretically-driven and developmentally-appropriate employment intervention aimed at increasing job seeking self-efficacy and readiness among YMSM and YTW of color ages 16-24.** Two formative assessment strategies will be used to determine the essential components of the employment intervention: (1) focus groups and (2) key informant interviews (Aim 1). First, focus groups be conducted with currently employed and unemployed (but seeking employment) YMSM and YTW. The goal of the focus groups will be to

explore and identify the following: perceived barriers to employment, beliefs in the benefit of employment, and career counseling needs of YMSM and YTW. Additionally, key components, including potential models of the adapted iFOUR employment curriculum will be shared and discussed with participants in order to gauge relevance and potential modifications for the target population. Next, we will conduct key informant interviews with YMSM, YTW, and LGBT-inclusive employers. The goal of this phase of formative research will be to hone and identify key areas related to barriers and facilitators to hiring and retaining YMSM and YTW: YMSM and YTW career readiness, identifying an inclusive employer, and post- placement support necessary to retain YMSM and YTW (Appendix II example interview guide).

**Focus Groups: Recruitment and Enrollment.** We will recruit up to 80 YMSM and YTW of color, ages 16-24, to participate in one of up to 10 focus groups .

**Key Informant Interviews: Recruitment and Enrollment.** We will recruit up to 64 key informant YMSM (up to 12), YTW (up to 12), and LGBT-inclusive employers (up to 40) to participate in key informant interviews. Over 35 major corporate employers in Chicago have a Corporate Equality Index of 100% (e.g., Groupon, Inc., McDonalds Corp., etc) (HRC, 2015).

**Aim 2: Review and adapt relevant intervention components from the existing evidence-based employment program for HIV-positive adults (iFOUR) to YMSM and YTW of color.**

**Convene a Community Advisory Board (CAB).** Up to a 12-member CAB of YMSM, YTW, youth-serving employment and vocational specialists, LGBT employment training and placement experts, and sexual health educators will be led by [name] and the investigative team. Members of the CAB will meet no less than 20 times over the course of the project to review and interpret qualitative findings into distinct curriculum adaptations. The CAB will be instrumental in providing information on curriculum content, appropriateness, cultural sensitivity and specificity, study methodology, and best methods for enhancing participation, as well providing ongoing feedback and interpretation of data. The CAB will ensure that the adaptations reflect YMSM's and YTW's experience and employment needs (Aim 2).

**Aim 3: Refine, pre-test, and pilot-test the employment intervention.** In order to achieve Aim 3, we will incorporate all qualitative findings and refine the final intervention curriculum modules using additional feedback from the CAB. In addition, the CAB will assist with Phase 2 by pre-testing and providing feedback on Phase 2 data collection instruments.

The adapted employment intervention will first be pre-tested (Baseline, workshops, Post-intervention) with an initial sample of up to 5 participants in order to test the implementation of assessments and workshop activities. Refinement to workshop activities will be considered if activities do not fit within the session time-period or participants do not understand or comprehend the activity.

Next, the intervention pilot-test of the final adapted employment intervention will be completed with a diverse sample of up to 70 YMSM and YTW, ages 16-24, in a single-arm longitudinal pre/post study of the employment intervention to evaluate *feasibility, acceptability, program satisfaction, and preliminary efficacy* using assessments at Baseline (T1), Post-Intervention (T2), and 8 Months Follow-Up (T3).

**Aim 4: Refine and pilot-test the intervention in community-based settings.** In order to achieve Aim 4, we will refine the procedures and intervention so that it may be conducted within community-based settings in order to further test the implementation of assessments and workshop activities in Phase 3.

The adapted employment intervention will be completed with a diverse sample of 40 YMSM and YTW, ages 16-24, in a single-arm longitudinal pre/post study of the employment intervention to evaluate *feasibility, acceptability, program satisfaction, and preliminary efficacy* using assessments at Baseline (T1), Post-Intervention (T2), and 3 Months Follow-Up (T3).

## 5.1 Intervention Enrollment Procedures

An ATN Study Identification number (SID) will be assigned by the site staff in consecutive order from the Carolina Data Acquisition and Reporting Tool (CDART).

## 5.2 Intervention/Investigation Procedures

Up to 70 participants will be enrolled for the intervention pilot part of phase 2 and up to 40 participants for phase 3. Participants will complete a 4 session workshop. Workshops will be in groups of 6-12. These workshops will be based on the pre-existing iFOUR program (description below) with modifications based on CAB, focus group, pre-test, and interviewer feedback.

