#### 5.2.4 Intervention Monitoring/Quality Control

Research staff running the workshops will complete fidelity assessments during administration of each workshop class to help ensure and evaluate homogeneity across workshop groups. In addition, workshop staff will conduct a debriefing session after the administration of each workshop class in order to note any issues or observations.

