#### Phase II and III

##### 10.3.1.1 Descriptive statistics

Descriptive statistics will be used to analyze the proportions and central tendencies for participant sociodemographic characteristics collected in the surveys completed by participants in the pilot-tests. We will first generate frequencies, means, and other measures of central tendency as appropriate to describe our sample and outcomes at each of the three time points (T1, T2, T3). Sensitivity analyses will be performed to address extreme outlying variables, including the removal of records with extreme outlying values from analyses.

Changes in primary and secondary outcomes between Baseline (T1) and Follow-Up (T3) will be assessed using paired t-tests for continuous variables and McNemar's test for categorical variables. Other statistical tests that appropriately account for the correlation in the dataset will be considered as needed. All hypothesis testing will be done at an alpha-level of 0.1, given the pilot/exploratory nature of the study.

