2.3. Sample Size Information

This study aims to enroll up to 70 participants with at least 50 of these participants completing the study (~70% retention rate). Given the exploratory nature of this study and limited access to this population, a power calculation was not performed. A repeated measures design was chosen to reduce the variability in the estimate of the treatment effect, at the expense of having a comparison group. In addition, practice or fatigue effects from repetition may affect certain outcomes (e.g. protean career attitudes scale and subscales). This trade-off was appropriate given the exploratory nature of a pilot study and the limited access to the study population.

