5. STATISTICAL ANALYSIS

5.1. General Considerations

The analytic plan is designed to determine preliminary efficacy of the intervention by comparing pre/post assessments of employment and sexual risk behaviors. Descriptive statistics will be used to analyze the proportions and central tendencies for participant sociodemographic covariates collected in the surveys. We will first generate frequencies, means, and other measures of central tendency as appropriate to describe our sample and outcomes at each of the three time points (baseline, post-intervention, and 8-month follow-up).

Changes in primary and secondary outcomes between baseline and 8-month follow-up will be assessed using paired t-tests for continuous variables and McNemar's test for matched categorical variables. We will use standard diagnostic tools to assess the appropriateness of the normality assumption (e.g., QQ-plots) and, if approximate normality of the residuals is not tenable, a non-parametric test for continuous paired data, i.e. Wilcoxon sign rank test will be used. All hypothesis testing will be done at an alpha-level of 0.1, given the exploratory nature of the study.

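### Workshops run in groups, but neither SAP allows for it: if change scores correlate within a workshop cohort, the paired tests do not hold their 10% level

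*Protocol*

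**What the plan says.** Protocol 5.2 sets both delivery and numbers: "Up to 70 participants will be enrolled for the intervention pilot part of phase 2 and up to 40 participants for phase 3", and "Workshops will be in groups of 6-12". Protocol 5.2.4 has workshop staff complete fidelity forms to help "evaluate homogeneity across workshop groups", so the protocol recognises that groups may differ. It handles this through forms and debriefing, not in the analysis.

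Section 5.1 of each SAP says that changes in outcomes will be "assessed using paired t-tests for continuous variables and McNemar's test for matched categorical variables", with a Wilcoxon signed-rank test as the fallback for continuous outcomes. It adds: "All hypothesis testing will be done at an alpha-level of 0.1". The adjusted models in SAP 5.4 and 5.5 list sociodemographics, workshop attendance, baseline employment and study completeness. They contain no workshop-group term, random effect or clustered standard error.

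The nearest provision is in Protocol 10.3.1.1: "Other statistical tests that appropriately account for the correlation in the dataset will be considered as needed". It names neither workshop groups nor a method, and neither SAP repeats it. Generalized estimating equations appear in the protocol's abbreviation list but nowhere else in the text supplied.

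**The concern.** A paired test deals with the correlation between one person's T1 and T3 scores. It does nothing about correlation between people. Participants who sit through the same sessions may change together. If they do, the mean change varies more from study to study than the paired standard error shows, and the test rejects too often.

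The outcomes most exposed are the continuous change scores: job-seeking self-efficacy and protean career attitudes (primary), and hours worked and sexual risk score (secondary). SAP 5.1 has already relaxed alpha to 0.10 because the study is exploratory. A further unstated inflation would make the preliminary efficacy signal look firmer than it is.

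**Working it through.** **Inputs from the documents.** Group size is 6-12, with up to 70 enrolled in Phase 2 and up to 40 in Phase 3 (Protocol 5.2). At least 50 of the 70 are expected to complete (Phase 2 SAP 2.3). Alpha is 0.10 (SAP 5.1). People who attend no workshop may still complete T3 (Protocol 6.3), and every T3 completer enters the change analyses (SAP 3.1).

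**Assumptions.** Tests are two-sided, since sidedness is not stated. The ICC of the change score is not given; it is taken as 0 to 0.10.

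**The plan's own figure.** 50/70 = 71.4%, which agrees with the stated retention of about 70%. No power calculation was done, so there is none to reproduce.

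**Groups and analysed size per group.** Phase 2: 70/12 = 5.8 to 70/6 = 11.7, so about 6 to 12 groups. With 71.4% retention, 6 × 0.714 = 4.3 to 12 × 0.714 = 8.6 are analysed per group. Phase 3: 40/12 = 3.3 to 40/6 = 6.7, so about 4 to 7 groups.

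**Formulas.** Design effect DE = 1 + (m − 1) × ICC, where m is the number analysed per group. Actual two-sided error = 2 × [1 − Φ(1.645/√DE)].

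Phase 2, 50 completers, m = 4.3 to 8.6:

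| ICC | DE | Effective N (50/DE) | Actual error | Simulated, 12 and 6 groups |
|---|---|---|---|---|
| 0 | 1.00 | 50 | 0.100 | 0.100, 0.102 |
| 0.01 | 1.03-1.08 | 48-46 | 0.106-0.113 | 0.105, 0.114 |
| 0.05 | 1.16-1.38 | 43-36 | 0.127-0.161 | 0.124, 0.162 |
| 0.10 | 1.33-1.76 | 38-28 | 0.154-0.215 | 0.156, 0.212 |

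Example: m = 8.57 and ICC 0.05 give DE = 1 + 7.57 × 0.05 = 1.379, √DE = 1.174, 1.645/1.174 = 1.401, error 0.161. The simulations used 40,000 runs per scenario.

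**Dilution by non-attenders.** Their number is an assumption. Take 6 groups of 7 plus 8 people with no group: N = 50 and Σm² = 6 × 49 + 8 = 302. Then DE = 1 + ICC × (302/50 − 1) = 1 + 5.04 × ICC. At ICC 0.05, DE is 1.25 and error about 0.14; at 0.10, DE is 1.50 and error about 0.18. Simulation with 6 groups of 6-7 plus 10 non-attenders gave 0.137 and 0.173.

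**Phase 3.** With all 40 analysed in 7 or 4 groups, simulated error was 0.14-0.17 at ICC 0.05 and 0.18-0.23 at 0.10. With 28 analysed in 4 groups (about 70% retention, assumed), it was 0.15 and 0.20.

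**McNemar.** Assuming 20% discordant pairs and 50 completers in 12 or 6 groups, the exact test ran at about 0.05 at ICC 0, 0.06-0.07 at 0.05 and 0.07-0.10 at 0.10. The asymptotic test ran at 0.10-0.11, 0.12-0.14 and 0.13-0.18. The SAPs do not say which is meant. The Wilcoxon fallback was not simulated; it makes the same independence assumption.

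**Candidate corrections, simulated at nominal 0.10.**

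- Cluster-robust standard error with t on (groups − 1) degrees of freedom, near-equal groups only: about 0.10 with 4 or 6 groups.
- The same method with non-attenders counted as single-person clusters: 0.124-0.130 (6 groups of 6-7 plus 10) and 0.136-0.152 (4 groups of 8 plus 8). The single-person clusters raise the degrees of freedom while a few large cohorts dominate the variance.
- CR2 standard error with Satterthwaite degrees of freedom: about 0.09-0.11 in the layouts tried, including unequal groups and single-person clusters.

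**The case against.** The strongest case on the other side is that nothing in the documents shows any within-cohort correlation. At an ICC of 0 the planned tests are correct, and at 0.01 the inflation is trivial. The primary objective in both SAPs is feasibility and acceptability, testing is labelled exploratory, and a single-arm design limits efficacy inference whatever the standard error. All of this stands. It makes the point conditional and moderate, but it does not supply a rule for handling cohort.

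Several stronger readings are tempting and are not supported:

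- *The p-values are too small.* That needs a positive ICC, which no document gives.
- *Actual error reaches 26%.* That figure takes ICC 0.10 and full groups of 12 with no dropout. The Phase 2 SAP plans on about 50 of 70 completing.
- *Confidence intervals will be too narrow.* The supplied text plans none. This applies only to intervals added at reporting.
- *McNemar results are equally affected.* Only the asymptotic version shows clear inflation over this ICC range.
- *The SAPs dropped a protocol commitment.* Protocol 10.3.1.1 names no clustering, and its sentence may mean repeated measures. Clustering is unspecified, not removed.
- *Each group shares one facilitator.* Protocol 5.2.3 says only that research team members facilitate.
- *The later trial will take its variance inputs from this pilot.* Protocol 2.4 says that the study leads to an intervention manual for that trial; it does not mention an ICC.

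A small number of cohorts is a fair warning against naive robust standard errors, as the simulations confirm. It is not a reason to leave cohort out, since a method that holds close to the nominal level is available.

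**Conclusion.** The gap is real: delivery is in groups, the named tests assume independent participants, and no cohort adjustment is prespecified in either phase. Its effect on the 10% level depends on an unknown ICC. It is negligible near 0.01 and material from about 0.05, where the continuous change tests would run at roughly 0.13-0.16 in Phase 2. At 0.10 they would run at roughly 0.15-0.22. Non-attenders who complete T3 bring the six-group figures down to about 0.14 and 0.17-0.18.

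These sizes rest on assumed ICCs, two-sided testing, a number of groups derived from 6-12 per group, and 71% retention. The finding supports adding a cohort-clustered analysis for the continuous outcomes. It does not support a claim that the planned results are wrong.

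**What to change.** In section 5.1 of both SAPs:

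1. Record the workshop cohort that each participant first joined. The attendance items described in SAP Appendix 1.2.1 show no cohort identifier, so one may have to be added from delivery records.
2. For each continuous change score, report a cohort-clustered analysis beside the unclustered paired test. Use either a CR2 standard error with Satterthwaite degrees of freedom, or a random cohort intercept with a small-sample degrees-of-freedom correction. Only the first was covered by the simulations above.
3. Do not use plain (groups − 1) degrees of freedom with non-attenders counted as single-person clusters; that runs at about 0.12-0.15.
4. Report the cohort ICC with its uncertainty, and note that 4 to 12 cohorts estimate it imprecisely.

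The cost is one paragraph per SAP, a cohort variable and a little programming. The statistical price is fewer degrees of freedom and wider intervals: with 6 equal groups the critical t is about 2.02, against 1.68 for 50 independent participants.
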